## CONFIDENTIAL

220104  
Protocol Amendment 1 Final

Procedure	Screening	Treatment Period 1			Treatment Period 2		Treatment Period 3			Early Withdrawal	Unscheduled	Notes
	D -14 to -1	D 1	D 2	D 3	D 4	D 5-14	D 15	D 16-17	D 18			
Serial PK sampling: GSK3036656•							X	X				PK samples collected predose (GSK3036656) and after dosing at 0.5, 1, 1.5, 2, 3, 4, 6, 8, 12, 24 hours relative to Day 15 dosing in Treatment Period 3. The Day 15 24 h sample must be taken prior to GSK3036656 dosing on Day 16.  The predose sample to be taken within 30 minutes prior to dose administration.  Blood is drawn for PK analysis at 0.5-4 hours ±5 minutes after dosing.  Blood is drawn for PK analysis at 6-12 hours ±20 minutes after dosing.  Blood is drawn for PK analysis at 24 hours ±1 hours after dosing.
AE review•		←-----→										AEs collected from the start of study intervention until day 18 of Treatment Period 3.
SAE review•		←-----→										SAEs collected from the signing of the ICF until Day 18 of Treatment Period 3.
Concomitant medication review•		←-----→										

AE = adverse event; D = Day; ECG = electrocardiogram; EE = ethinyl estradiol; LNG = levonorgestrel; PK = pharmacokinetic; SAE = serious adverse event.

Assessments performed predose on Day 4 of Treatment Period 2 were considered baseline for GSK3036656 dosing.

- Is used to indicate a study procedure that requires databasing (either in eCRF, laboratory or other third-party vendor).
- Is used to indicate a study procedure that does not require databasing (in source only).
- Participants may be admitted the night before Day 1 and Day 14, but study procedures will commence on the morning of Day 1 and morning of Day 15.

## 2. INTRODUCTION

### 2.1. Study rationale

GSK3036656 is being developed for TB and a Phase 2B/C regimen building and duration ranging study conducted under the UNITE4TB consortium is planned to start in 4Q2023.

GSK3036656 was teratogenic in rats and rabbits. In rats (most sensitive species) the NOAEL for embryofetal effects was [REDACTED] mg/kg/day, with an exposure (AUClast) at this dose level of [REDACTED] µg.h/mL which is at parity with the [REDACTED] mg clinical dose. Precautions will therefore be required prior to starting WOCBP on GSK3036656. The nature of these precautions will be subject to discussion with the external TB community, patient groups and regulators at the time of file.

[figure not shown]
Of the 10.6 million TB patients diagnosed each year, approximately twenty percent are WOCBP. Therefore, there exists the potential for broad use and impact of GSK3036656 containing regimens regardless of any label restrictions. In addition, several potential combination TB drugs carry label restrictions for pregnancy and WOCBP, whilst TB itself poses risks in pregnancy to both the mother and the developing foetus.

Based on the in-vitro data, GSK3036656 does not exhibit any induction or inhibition of key cytochrome P450s (CYPs). To minimize any risk due to the teratogenicity observed in rats and rabbits, ongoing and planned clinical development studies including GSK3036656 currently mandate use of non-user dependent contraception (intrauterine contraceptive device, or implantable or depot injectable progesterone) during the study for female study participants of childbearing potential, or recruitment of women of non-childbearing potential. In addition, highly sensitive pregnancy testing must be performed prior to dosing and throughout the studies. The recommended population to be enrolled into clinical drug interaction studies with combined oral contraceptives are postmenopausal and premenopausal females (if studying PD endpoints) [FDA, 2023]. Taking into account the unknown DDI interaction between GSK3036656 and Microgynon, contraception should not be considered as effective, therefore enrollment of only WOCBP in this study is a safety pregnancy-specific risk minimization measure [EMA, 2022].

FDA guidance states that if an investigational drug shows any nonclinical reproductive and developmental toxicity, then an OC clinical DDI study waiver would be unlikely to be granted by regulators, meaning that an OC DDI study would be required for GSK3036656 as part of the marketing authorization submission. In addition, as non-user-dependent contraceptive measures may not be available or culturally acceptable in some of the participating countries in the Phase 2B/C study, there is a risk that recruitment will be negatively affected, and WOCBP who need access to TB treatment will not be eligible for the study. Hence the opportunity of user dependent contraception with an OC could exclude fewer WOCBP with TB by offering more choice.

Conducting an OC DDI study in parallel with Phase 2B could be beneficial as this could potentially generate data that could allow the use of less restrictive contraceptive measures during Phase 2C, which would have a positive impact on recruitment. There are other regimens within the study that do not require these stringent contraception restrictions and these are only being imposed because of GSK656-containing regimens.

CCI

## 2.2. Background

TB remains a concerning health problem, with *Mycobacterium tuberculosis* (Mtb) now causing more deaths than HIV/ AIDS. In 2021, 1.6 million people died from TB, making it the leading bacterial infectious disease killer in the world [EMA, 2022;FDA, 2023; WHO, 2022] The current long-standing first-line antituberculosis agents are relatively ineffective in controlling the TB epidemic in high-burden countries. Treatment takes 4-18 months to complete (depending on drug sensitivities of the isolated strain and availability of shorter regimens) and is associated with side effects resulting in poor compliance which leads to treatment failure and an increased likelihood of developing drug-resistance.

The development of new drug combinations that are effective against drug-resistant strains of Mtb, and that have the potential to shorten the duration of TB treatments offers the hope of tackling the TB pandemic. A new treatment regimen requires at least three different drugs to which no clinical resistance exists. This highlights the need for the development of additional new chemical entities that strike an appropriate balance between antituberculosis activity and safety profiles, a balance that will enable new future drug combinations that make the optimal use of previously developed entities.

GSK3036656 is a compound with a novel mechanism of action under development for the treatment of TB. It suppresses protein synthesis in Mtb by selectively inhibiting the enzyme Leucyl t-RNA synthetase.

CCI

██████████ and the drug shows potent activity in animal models, resulting in very low predicted efficacious human doses. *In vitro* data show that the risk of drug-drug interactions with GSK3036656, either as perpetrator or victim, is low. These factors make GSK3036656 an attractive potential candidate for the treatment of tuberculosis.

Conducting this OC DDI study will provide data showing if there is any pharmacokinetic effects of GSK3036656 on a combined oral contraceptive, which, in conjunction with cultural sensitivities in specific regions, will help inform future studies on suitable contraceptive measures to be used.

A description of the chemistry, nonclinical and clinical data generated to date for GSK3036656 is provided in the IB.

### **2.3. Benefit/risk assessment**

Data described in the IB support the safety profile of the selected dose of GSK3036656 in patients with newly-diagnosed TB and healthy volunteers. The known potential risks associated with GSK3036656 can be appropriately mitigated by the careful selection of study participants and the proposed safety monitoring procedures. Routine safety and tolerability will be evaluated from reported AEs, scheduled physical examinations, vital sign measurements, 12-lead ECGs, and clinical laboratory test results as well as observation by clinical staff. The potential risks associated with the administration of GSK3036656 are considered to be justified by the potential benefits that may be afforded to patients with TB if this and future studies with GSK3036656 are deemed successful for the participants from the study treatment. More detailed information about the known and expected benefits and risks and reasonably expected AEs of GSK3036656 may be found in the IB.

### 2.3.1. Risk assessment

The Sponsor's assessment of known and potential risks of GSK3036656 is summarized in [Table 2](#).

**Table 2 Summary of Potential Risks of Clinical Significance**

Potential Risk of Clinical Significance	Summary of Data/Rationale for Risk	Mitigation Strategy
Study Intervention(s) GSK3036656		
Reduction in red blood cell count	
Non-Clinical
 
In a 4-week rat study (doses CCI [REDACTED] mg/kg/d) - dose-dependent decline in reticulocytes (by up to 52% in males and 62% in females) at day 7 followed by normal levels by day 14 and increased levels by day 29/30 compared to controls. Hgb levels decreased by 10-13% compared to controls on day 14 and day 29/30.
 
In a 4 week dog study (doses CCI [REDACTED] mg/kg/d) - mild dose-dependent decrease in Hgb on day 14 (by about 10% compared to controls) with recovery by week 4. Reticulocyte counts unaffected. Dogs not bled on day 7.
 
No histopathological changes in bone marrow or other relevant histopathology in the 4-week studies.
	
Standard safety haematology and clinical chemistry assessments will be performed and both trends and changes outside normal range will be monitored as part of laboratory safety assessments.
 
Participants whose haemoglobin drops below pre-specified limits will be withdrawn from study intervention (Section 7.1.3).
 
Haematology Stopping Criteria have been implemented as described in Section 7.1.3:

Potential Risk of Clinical Significance	Summary of Data/Rationale for Risk	Mitigation Strategy
	
Clinical
 
In the study 201040 (FTIH) a possible trend of decreased haemoglobin from baseline to follow-up was noted in aggregate haematology data. The mean change from baseline to follow-up was -4.9 g/L in the CD mg repeat dose cohort, compared to -1.5 g/L in the placebo group. None of the values hit PCI criteria, and declines were not clinically relevant.
 
No clinically significant trends in reticulocyte values were observed, and there were no values of potential clinical importance reported for reticulocytes.
 
In the Study 201214 no significant trends in the haemoglobin level or reticulocytes count were observed.
	

Heart valvular and vascular pathology	
Non-Clinical
 
In a 7-day dog dose range finding study – minimal focal subendocardial haemorrhage on the atrial surface of the left atrioventricular valve observed in both animals at the top dose of [REDACTED] mg/kg/d.
 
In a 10-day dog investigative study at [REDACTED] mg/kg/d – vascular lesions (including minimal focal necrosis and inflammatory infiltrate) in 3 out of 8 dogs.
 
In the 4-week dog GLP study - no heart or valve changes were observed up to the top dose of [REDACTED]
	
Valvular pathology can be monitored in humans with non-invasive echocardiography, these will be performed at screening.
 
Vascular pathology is not readily monitorable in humans.
 
Subjects with history of known cardiac valve abnormalities, any significant arrhythmia or ECG finding are not eligible for the study.
 
To avoid risk to study participants, dosing will be limited to doses at which individual exposures do not exceed AUC0-24 and Cmax to [REDACTED] <math>\mu g.h/mL</math> and [REDACTED] <math>\mu g/mL</math>, respectively.

Potential Risk of Clinical Significance	Summary of Data/Rationale for Risk	Mitigation Strategy
	
CCl mg/kg/day and there was no increase in inflammatory markers.
 
In the 17-week GLP dog study there were no heart or valve changes up to the top dose of CCl mg/kg/day.
 
In the 17-week rat study there were no changes in cardiac pathology up to the top dose of CCl mg/kg/day.
 
Valvular or vascular pathology were not observed in rats. This pathological change is not commonly seen in animals, and its mechanism and significance to humans are not clear. A correlation between the presence of hemodynamic changes and the presence of this pathology is suspected, but currently unproven.
 
Clinical
 
Echocardiograms were performed at screening and follow up in the 201040 FTIH study in order to exclude participants with pre-existing valve or other cardiac abnormalities from the study, and to detect the presence of abnormalities after completion of the study. No abnormalities were detected.
 
No SAEs, or AEs of cardiovascular nature were reported. There was no change from baseline in
	
These exposures are 10-fold below the lowest NOAEL achieved in the 17-week studies (rat) QTc stopping criteria have been implemented as described in Section 7.1.2.

Potential Risk of Clinical Significance	Summary of Data/Rationale for Risk	Mitigation Strategy
	
heart rate observed at any dose. No trends in blood pressure change were observed. Cardiac telemetry and echocardiogram-related interpretations were within normal range. There were no clinically significant ECG observations. There were no troponin I abnormalities in participants after receiving study drug.
 
In Study 201214, one subject (dose CC mg) had drug-related ventricular hypokinesia. One subject (dose CC mg) had decreased ejection fraction. None of the participants met the QTcF stopping criteria. No SAEs of cardiovascular nature were reported.
	
Hemodynamic changes	
Non-Clinical
 
Hemodynamic changes in several studies at <math>\geq</math> CC mg/kg in rats and <math>\geq</math> CC mg/kg in dogs - increased heart rate (rats and dogs), increased (rats) or decreased (dogs) blood pressure.
 
Clinical
 
Data from the 201040 (FTIH) and 201214 studies showed no significant changes in vital signs assessments during the study, and no clinically significant changes in ECG or telemetry assessments including QTc and PR intervals.
	
Vital signs will be monitored throughout the study as described in Section 8.3.2.
 
ECGs will be monitored throughout the study as described in Section 8.3.3.
 
QTc stopping criteria have been implemented as described in Section 7.1.2

Potential Risk of Clinical Significance	Summary of Data/Rationale for Risk	Mitigation Strategy
GSK3036656 is cleared through the kidneys	
Analysis of the 201040 FTIH study data showed the main route of clearance for GSK3036656 is renal and there is therefore a risk that participants with low creatinine clearance may accumulate GSK3036656 and exceed predefined exposure limits. Participants with creatinine clearance less than 75 mL/min were excluded from the 201214 study.
	
Participants with an estimated creatinine clearance less than 75 mL/min will be excluded.

Skin depigmentation	
Non-Clinical
 
In a 17-week dog toxicology study (doses CCI CCI mg/kg /day): loss of pigmentation on the eyelids, nose or muzzle of all animals at 45 mg/kg/day group CCI ug.h/mL) and most animals in the CCI mg/kg/day group CCI ug.h/mL). PNL-2 (a melanocyte marker) immunohistochemistry staining demonstrated moderate cytoplasmic positivity in a population of cells in the basal region of the epidermis (interpreted to be melanocytes). The decreased pigmentation was therefore not associated with a loss of melanocytes in affected animals on immunohistochemistry. Depigmentation was not observed in the CCI mg/kg/day group (CCI ug/h/mL). Depigmentation was not observed in the two previous 4 week dog toxicology studies up to CCI mg/kg/day CCI ug.h/mL).
	
The duration of dosing in this study (14 days) is shorter than that used in the dog toxicology study and the maximum exposure (AUC0-24) has been capped at CCI ug.h/mL (10-fold below effect level for loss of pigment in the 17-week dog study).
 
The physical examination of study participants will include visual examination of the skin.
 
Participants with vitiligo will be excluded from the study to avoid confounding skin assessment at baseline and follow-up physical examinations.

Potential Risk of Clinical Significance	Summary of Data/Rationale for Risk	Mitigation Strategy
	
Clinical
 
No adverse events were reported in the 201040 (FTIH) and 201214 studies that would be considered consistent with an asset-related depigmentation.
	
Developmental toxicity	
Non-Clinical
 
Embryofetal developmental effects were observed in both rat and rabbit. In the rat, reduction in fetal viability and malformation, including skeletal malformations, ventricular septal defects and cleft palate were observed from [REDACTED] mg/kg/day. The NOAEL for embryofetal effects in the rat is [REDACTED] mg/kg/day, the exposure (AUClast) at this dose level is [REDACTED] µg.h/mL which is at parity with the [REDACTED] mg clinical dose. In the rabbit, the only test article-related fetal abnormality was an increase in the incidence of full thoracolumbar ribs. The NOAEL for effects on rabbit embryofetal development was [REDACTED] mg/kg/day, and the AUClast at this dose was [REDACTED] µg.h/mL.
 
Clinical
 
Studies 201040 (FTIH) and 201214 excluded females.
	
For the study, only WONCBP will be eligible:
 
 
Participants with documented infertility (hysterectomy, bilateral salpingectomy, bilateral oophorectomy, other alternative documented)
 
Postmenopausal females (no menses for 12 months without an alternative medical cause + high FSH)
 
 
Pregnancy testing has been implemented as described in Section 8.3.5.

Potential Risk of Clinical Significance	Summary of Data/Rationale for Risk	Mitigation Strategy
Study Procedures		
Blood draws	Venous access in some participants may be problematic and the needles used may cause bruising (ecchymosis) around the access site.	
A maximum of approximately 160 mL of whole blood will be collected over the course of the study.
 
At visits to collect whole blood samples, one or more samples of sufficient volume will be collected and divided into suitable portions for the various analyses.
 
Whole blood samples will be collected by site personnel experienced in phlebotomy.

MICROGYNON 30 (Microgynon) [Microgynon, 2023]. Summary of Product Characteristics, 2023		
Circulatory disorders: risk of venous thromboembolism (VTE) and arterial thromboembolism (ATE)	
Epidemiological studies have suggested an association between the use of COCs containing ethinylestradiol and an increased risk of arterial and venous thrombotic and thromboembolic diseases such as myocardial infarction, stroke, deep venous thrombosis, and pulmonary embolism. These events occur rarely in average-risk women.
 
The use of any combined hormonal contraceptive increases the risk of VTE compared with no use. Data from a large, prospective 3-armed cohort study (EURAS1 and LASS2) suggest that this increased risk is mainly present during the first 3 months. VTE
	
For the study, eligible participants who are healthy as determined by the investigator or medically qualified designee based on a medical evaluation including medical history, physical examination, laboratory tests, and cardiac monitoring (history and ECG), non-obese, non-smokers, which exclude presence of major risk factors for both VTE and ATE.
 
Eligible subjects > 35 years old will be more carefully monitored for clinical symptoms of ATE.

Potential Risk of Clinical Significance	Summary of Data/Rationale for Risk	Mitigation Strategy
	
may be life-threatening or may have a fatal outcome (in 1-2% of cases).
 
Epidemiological studies have associated the use of CHCs with an increased risk for arterial thromboembolism (e.g. myocardial infarction, angina pectoris, stroke or TIA). Arterial thromboembolic events may be fatal.
	
Echocardiography has been implemented at screening as defined in Section 8.3.6.
 
Full physical examination with vital signs, ECG and laboratory tests have been implemented as described in Section 8.3.

Tumors	
A meta-analysis from 54 epidemiological studies reported that there is a slightly increased relative risk (RR = 1.24) of having breast cancer diagnosed in women who are currently taking COCs. These studies do not provide evidence for causation. The observed pattern of increased risk may be due to an earlier diagnosis of breast cancer in COC users, the biological effects of COCs or a combination of both.
 
In rare cases, benign liver tumours, and even more rarely, malignant liver tumours have been reported in users of COCs.
	
Exclusion criteria have been added to exclude subject with major health conditions (including tumors) as described in Section 5.2.
 
Full clinical examination is a part of the standard safety monitoring for the study.
 
Short duration of dosing by COCs mitigates this risk.

Metabolic problems: lipid and glucose abnormalities	
Women with hypertriglyceridaemia, or a family history thereof, may be at an increased risk of pancreatitis when taking COCs.
 
Although COCs may have an effect on peripheral insulin resistance and glucose tolerance, there is no evidence for a need to alter the therapeutic regimen in women with
	
Subjects with baseline problems are eligible if relevantly compensated.
 
Lipid and glucose metabolism safety monitoring have been implemented as described in Section 10.2 Appendix 2.

Potential Risk of Clinical Significance	Summary of Data/Rationale for Risk	Mitigation Strategy
	diabetes taking low dose COCs (containing < 50 µg ethinylestradiol). However, women with diabetes should be carefully observed while taking COCs.	
Hypertension	Small increases in blood pressure have been reported in many women taking COCs, clinically relevant increases are rare. However, if a sustained clinically significant hypertension develops during the use of a COC, it is prudent for the doctor to withdraw the COC and treat the hypertension. Where considered appropriate, COC use may be resumed if normotensive values can be achieved with antihypertensive therapy	Vital signs monitoring have been implemented as described in Section 8.3.2
Gastrointestinal tract problems	Nausea, diarrhoea, abdominal pain and vomiting were reported in COCs users	Full clinical examination and vital signs are a part of the standard safety monitoring as described in Section 8.3.
Liver problems	Acute or chronic disturbances of liver function may necessitate the discontinuation of COC use until markers of liver function return to normal. Recurrence of cholestatic jaundice which occurred first during pregnancy or previous use of sex steroids necessitates the discontinuation of COCs	Exclusion criteria have been added to exclude participants with hepatitis B, C, impaired LFTs (ALT and Bilirubin >1.5 x ULN) and those with the history of regular alcohol consumption within 6 months. LFT is a part of the standard safety monitoring as described in Section 10.2  Liver stopping criteria have been implemented as described in Section 7.1.1.

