##### Type of Participant and Disease Characteristics

2. Participants who are healthy or compensated as determined by the investigator or medically qualified designee based on a medical evaluation including medical history, physical examination, laboratory tests, and cardiac monitoring (history and ECG).
3. A creatinine clearance  $\geq 75$  mL/min (Cockroft-Gault formula).
4. Normal echocardiogram or echocardiogram with normal left ventricular function with at most trace to mild valvular regurgitation is allowed and no valvular stenosis.

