## **5.2. Exclusion criteria**

**Participants are excluded from the study if any of the following criteria apply:**

### **5.2.1. Medical History**

1. History of known cardiac valve abnormalities

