### **5.2.2. Laboratory Assessments**

2. Presence of hepatitis B surface antigen at Screening or within 3 months prior to starting study treatment.
3. Positive hepatitis C antibody test result at Screening or within 3 months prior to starting study treatment AND positive on reflex to hepatitis C RNA.
4. Positive HIV-1 and -2 antigen/antibody immunoassay at Screening.
5. Alanine aminotransferase (ALT)  $>1.5 \times \text{ULN}$ . A single repeat of ALT is allowed within a single screening period to determine eligibility.
6. Bilirubin  $>1.5 \times \text{ULN}$  (isolated bilirubin  $>1.5 \times \text{ULN}$  is acceptable if bilirubin was fractionated and direct bilirubin  $<35\%$ ).

7. Any acute laboratory abnormality at Screening which, in the opinion of the investigator, should preclude participation in the study of an investigational compound.
8. Participants with haemoglobin <8.0 g/dL
9. Any Grade 2 to 4 laboratory abnormality at Screening, with the exception of creatine phosphokinase and lipid abnormalities (e.g., total cholesterol, triglycerides, etc), and ALT (described above), excludes a participant from the study unless the investigator provided a compelling explanation for the laboratory result(s) and has the assent of the sponsor. A single repeat of any laboratory abnormality is allowed within a single screening period to determine eligibility.
10. A positive test result for drugs of abuse (including marijuana), alcohol, or cotinine (indicating active current smoking) at Screening or before the first dose of study treatment.

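### The protocol's risk table says tumour exclusions were added in Section 5.2, but none of the 23 exclusions names a tumour; thrombosis history rests on investigator judgement

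*Protocol*

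**What the plan says.** Table 2 in Protocol Section 2.3.1 lists the risks of Microgynon with a mitigation for each. Three rows matter here.

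- **Tumours.** The mitigation reads "Exclusion criteria have been added to exclude subject with major health conditions (including tumors) as described in Section" 5.2. The row adds clinical examination and the short duration of dosing.
- **Circulatory disorders.** Eligible women are described as healthy on the investigator's medical evaluation, non-obese and non-smoking, "which exclude presence of major risk factors for both VTE and ATE". The row adds closer watching for arterial symptoms above age 35, a screening echocardiogram and the general safety assessments. It points to no exclusion in Section 5.2.
- **Liver problems.** This row uses the same form of words as the tumour row: "Exclusion criteria have been added to exclude participants with hepatitis B, C, impaired LFTs", followed by the limits and an alcohol criterion.

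Section 5.2.1 (Medical History) holds a single exclusion: "History of known cardiac valve abnormalities". Inclusion criterion 2 in Section 5.1 admits "Participants who are healthy or compensated as determined by the investigator or medically qualified designee", on the basis of medical history, examination, laboratory tests and cardiac monitoring.

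**The concern.** An ethics committee or investigator who reads Table 2 will take it that Section 5.2 contains a tumour exclusion. If it does not, the risk assessment credits the study with a control it lacks.

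The thrombosis row raises a softer question: whether the criteria deliver the assurance the row gives. The women may be up to 65 years old, most are expected to be postmenopausal (rationale for Amendment 1), and they gain nothing personally (Section 2.3.2). Table 2 itself says that venous and arterial events can be fatal. Collection of adverse events ends on Day 18, three days after the second tablet, and Section 8.4.1 does not require investigators to look actively for later events. Selection therefore carries much of the protection.

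The stake is participant safety and the accuracy of the risk assessment. The estimate of the drug interaction is not at stake.

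**Working it through.** No formula applies; the check sets the table's statements beside the criteria.

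**Step 1: the exclusion list.** By subsection, 5.2.1 has 1, 5.2.2 has 9, 5.2.3 has 4, 5.2.4 has 2, 5.2.5 has 2 and 5.2.6 has 5. The sum is 1 + 9 + 4 + 2 + 2 + 5 = 23. The numbering runs 1 to 23 unbroken, so no criterion is lost from the text.

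**Step 2: what each row promises and what is there.**

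| Table 2 row | What it relies on | What the criteria contain |
|---|---|---|
| Liver | Added exclusions: hepatitis B, hepatitis C, ALT, bilirubin, alcohol | Exclusions 2, 3, 5, 6 and 21: 5 of 5 named |
| Tumours | Added exclusions in Section 5.2, tumours included | 0 of 23 name a tumour |
| Circulatory | Investigator's health evaluation, non-obese, non-smoking | Inclusion 2; inclusion 5 (BMI at most 31.0); exclusions 10 and 22 |

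The first part of the tumour sentence is partly met. Section 5.2 does exclude some major conditions, such as HIV, and hypertension or type 2 diabetes that needs more than diet and exercise. The part about tumours is not met. The liver row shows that the same wording elsewhere in the table does lead to named criteria.

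**Step 3: thrombosis history.** None of the 23 exclusions names previous venous or arterial thromboembolism or a clotting disorder. Besides inclusion 2, nine rules bear on thrombotic risk or its consequences:

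- Inclusion 5 limits BMI.
- Exclusions 10 and 22 cover smoking.
- Exclusion 20 covers hypertension and type 2 diabetes.
- Exclusion 17 covers ECG findings.
- Inclusion 4 asks for a normal echocardiogram or an "echocardiogram with normal left ventricular function" and limited valve findings, which may catch some cardiac consequences.
- Exclusion 11 by default removes a woman who cannot stop a drug taken for a thrombotic condition, subject to case-by-case permission.
- Exclusion 7 covers "Any acute laboratory abnormality at Screening which, in the opinion of the investigator, should preclude participation in the study of an investigational compound".
- Exclusion 9 covers graded laboratory abnormalities.

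Take a woman with an old, untreated deep vein thrombosis and normal screening tests. She meets no named exclusion. Whether she enters depends on the judgement under inclusion 2.

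**Step 4: the wording of that judgement.** The circulatory row assumes women who are healthy. Inclusion 2 also accepts women who are compensated. The gate is therefore wider than the one the row describes.

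**Step 5: exposure.** Each woman takes one tablet on Day 1 and one on Day 15. That is 2 × 0.03 mg = 0.06 mg ethinylestradiol and 2 × 0.15 mg = 0.30 mg levonorgestrel. About 20 women are planned (Section 9.5), so about 40 tablets in all.

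**The case against.** The strongest reply is that only one cross-reference is faulty. The circulatory row never says that Section 5.2 contains a thrombosis exclusion. It names a mechanism, and every part of that mechanism is in the criteria. A reader might infer that both rows point to exclusions that are missing. The documents support this for tumours only.

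A reader might also infer that women with a past thrombosis or cancer will be enrolled. The documents do not show this. The investigator takes a medical history and can find such a woman not healthy. Section 2.3.2 describes the population as having no significant medical history, which tells the investigator how to read inclusion 2. That sentence is not a numbered criterion, however, and inclusion 2 lists no conditions.

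A third inference is that a positive antiphospholipid antibody result has no route into eligibility. The test is in the laboratory panel (Table 10) and no criterion names it. But inclusion 2 makes laboratory tests part of the health evaluation, and Section 8 requires all screening evaluations to be reviewed for eligibility. Automatic exclusion on a positive result would be a preference, and the documents offer no evidence for it.

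Finally, the documents list no contraindications to Microgynon and do not say which risk factors they regard as major. Treating past thromboembolism or a clotting disorder as one is a clinical assumption. These replies reduce the thrombosis part to a suggested improvement. They do not make the tumour statement true.

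**Conclusion.** The tumour statement in Table 2 is wrong as written: 0 of 23 exclusions name a tumour. This is a discrepancy between the risk assessment and the eligibility criteria, and it should be corrected.

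The thrombosis statement is not contradicted, because its stated elements exist. Its assurance is not guaranteed either: 0 of 23 exclusions name past thromboembolism or a clotting disorder, and such a history rests on a judgement that admits compensated women. This part assumes that such a history counts as a major risk factor.

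Absolute risk is probably small, given two single tablets, about 20 women and the monitoring in Table 2. The documents do not say how many women might be affected. The primary pharmacokinetic analysis and the sample size are untouched.

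**What to change.** Add to Section 5.2.1:

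1. The tumour exclusion that Table 2 says is already there, for example current or past breast cancer or liver tumour, the types the tumour row mentions. The minimum alternative is to correct the sentence in Table 2, but that leaves the safeguard absent.
2. As a cheap improvement, a history of venous or arterial thromboembolism or a known clotting disorder. Section 5 bars waivers, so a named exclusion would bind where a general judgement does not.

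Leave antiphospholipid antibody results to investigator review under inclusion 2; no automatic exclusion is needed.

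The cost is a protocol amendment with IRB/IEC approval, and health authority approval if it is substantial (Section 10.1.1). No new test or visit is needed, since medical history is already taken (Section 8.1.2). There may be a few more screen failures, who may not be rescreened (Section 5.4); the documents give no basis for a number.
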